# **10.3 WITHDRAWAL FROM THE TRIAL**

The patient will be free to withdraw from the trial at any time without giving reasons and without prejudicing any further treatment/care.

In line with usual clinical care, cessation or alteration of treatment regimens at any time will be at the discretion of attending clinical teams or the patients themselves. Where patients wish to withdraw from the trial, clarification of the extent of withdrawal will be sought and documented in the eCRF. It will be possible for patients to withdraw from future study questionnaires but still have follow up through review of electronic records and/or linkage with NHS England and Public Health Scotland.

#### **10.4 INTERNAL PILOT**

The internal 9-month pilot phase will test trial processes including recruitment and adherence. During the internal pilot detailed screening data will be collected from each site to determine the factors which are impacting recruitment, in addition to online discussions with the Principal Investigator at each site.

# **11. ASSESSMENTS/DATA COLLECTION**

Participating sites will be expected to maintain a file of essential trial documentation (Investigator Site File) and to complete all electronic Case Report Forms (eCRFs) for the trial.

# **11.1 SUBMISSION OF TRIAL DATA**

#### Electronic Case Report Forms (eCRF)

Trial data will be recorded by trial site research staff in the trial-specific eCRF designed and administered by the Robertson Centre for Biostatics (RCB) at the University of Glasgow. The participant's trial number plus full name, date of birth, postcode, email address, NHS number and CHI number in Scotland (for long term data linkage via NHS databases) and initials will be added to the eCRFs in order to identify the participant. This will be stored separately to clinical results, reports and demographic data, which will be pseudonymised with the patient's unique trial number. A query management tool within the eCRF will highlight to sites any missing or discrepant data queries.

# **11.2 BASELINE DATA**

#### Baseline data (up to 6 months prior to randomisation):

- Demographics
- Medical History
- Questionnaires including EQ-5D-5L, KCCQ and resource use
- Medication (diuretic and 4 heart failure drugs only, no doses, from electronic patient records)
- Haemoglobin, eGFR, HbA1c, NTproBNP (if available),
- ECG: Atrial fibrillation, LBBB and upload
- Echocardiogram: LVEF and report upload

#### Ethnic diversity and inclusivity

• This trial will be inclusive of all patients affected by heart failure and in order to monitor this we will collect data on sex, ethnicity, occupation, living arrangements, education level, distance to nearest hospital, total household annual income.

# 11.3 FOLLOW UP

Patients will be followed up for a minimum of 12 months. Follow up will continue until 1 year after the last patient is randomised. This duration has previously been used in effectiveness trials of cardiovascular imaging .

#### 6 month follow-up (± 28 days):

- Imaging report upload
- Questionnaires: EQ-5D-5L, KCCQ and acceptability (online, phone or post).
- Medication (as per baseline)
- Resource use (from review of electronic records):
  - Any other cardiac tests (stress CMR, CTCA, ICA)
  - Hospitalisation for cardiovascular cause (Days in CCU/Days in HDU/Days in ICU/Days in General Ward)
  - Outpatient appointments (cardiology or cardiothoracic surgery)

#### 12 month follow-up (± 28 days):

- Any of the following events occurred from review of electronic records (category code list):
  - Death cause if known
  - $\circ$  Revascularisation:
    - PCI: Date of PCI Elective/urgent Planned (Yes/No) CABG: Date of PCI Elective/urgent

#### Planned (Yes/No)

- Imaging report upload
- Questionnaires: EQ-5D-5L and KCCQ, resource use (online, phone or post)
- Medication (as per baseline)
- Resource use (from review of electronic records):
  - Any other cardiac tests (eCRF category code list stress CMR, CTCA, ICA)
  - Hospitalisation for cardiovascular cause (category code list Days in CCU/Days in HDU/Days in ICU/Days in General Ward)
  - o Outpatient appointments (cardiology or cardiothoracic surgery)

#### Annual follow-up (± 28 days):

- Any of the following events occurred from review of electronic records (category code list):
  - Death cause if known
  - Revascularisation:
    - PCI: Date of PCI

Planned (Yes/No)

CABG: Date of PCI

Planned (Yes/No)

- Imaging report upload
- Questionnaires: EQ-5D-5L
- Echocardiogram LVEF and report upload

- Resource use (from review of electronic records) :
  - Any other cardiac tests (eCRF category code list stress CMR, CTCA, ICA)
  - Hospitalisation for cardiovascular cause (category code list Days in CCU/Days in HDU/Days in ICU/Days in General Ward)
  - Outpatient appointments (cardiology or cardiothoracic surgery)

# Longer-term follow-up (by remote data linkage with NHS records pending additional funding) for up to 10 years:

- Any of the following events occurred (category code list):
  - Death cause if died
  - o Myocardial infarction
  - o Heart failure hospitalisation
  - Revascularisation:
    - PCI: Date of PCI
      - Planned (Yes/No)

CABG: Date of CABG

Planned (Yes/No)

#### Standard unscheduled CRFs:

- Withdrawal
- Serious Adverse Events (angiography complications and contrast reactions only)
- Death

#### **11.4 SCAN UPLOAD**

Study scans (ICA, CTCA, stress CMR) will be transferred to a central corelab at University of Leeds intermittently (e.g. every 6 months). These scan results will be used for future sub-studies (which will be subject to their own ethical and other approvals). The corelab analysis will not be used to influence decisions into how trial patients are managed but only for future research purposes.

#### **11.5 LONG TERM FOLLOW UP**

Individual sites will seek, for all randomised patients, the certified causes of death from medical records, the ONS or NHS England (England)/Public Health Scotland. Notification of deaths is independent of the patients' clinical follow-up (if they remain resident in the United Kingdom).

Details of late cardiovascular events (including Acute Coronary Syndrome, acute or planned revascularisation procedure, any heart failure hospitalisation) beyond the 12-month follow-up period may be obtained from hospital and GP records or from centralised NHS databases for a period of up to 10 years. An amendment will be submitted to the HRA to extend the study beyond the 5-year study period, when additional funding has been awarded.

#### **11.6 DEFINITION OF END OF TRIAL**

The end of the trial is defined as the date of last randomised patient has reached the minimum 12m follow up.

#### **11.7 SCHEDULE OF EVENTS**

	Eligibility	Baseline	Six months post randomisation	One year post randomisation	Annual follow-up	Long term data linkage
Usual Care						
Demographics and medical history	х					
LVEF Assessment	х					
Blood results (Hb, eGFR, HbA1c, NTproBNP if available)		x				
Electrocardiogram		х				
Echocardiogram upload		х			х	
Imaging Result upload (CTCA, stress CMR, ICA)			x			
Cardiac medication		х	х	х		
Research Activities						
Consent	х					
Confirmation of eligibility	х					
EQ-5D-5L questionnaire		х	х	х	х	
KCCQ questionnaire		х	х	х		
Resource use		х		х		
Acceptability questionnaire			x			
Primary endpoint			х	х	х	x
Secondary endpoint			х	х	х	
SAEs			x	х	x	

# **12. SERIOUS ADVERSE EVENTS PROCEDURES 12.1 GENERAL DEFINITIONS**

A Serious Adverse Event (SAE) is defined in general as "any untoward medical occurrence or effect" that:

- results in death,
- is life-threatening\*,
- requires inpatient hospitalisation or prolongation of existing hospitalisation,
- results in persistent or significant disability or incapacity,
- consists of a congenital anomaly or birth defect,
- may jeopardise the patient and may require medical or surgical intervention to prevent one of the outcomes listed above.

\*the term life-threatening refers to an event in which the patient was at risk of death at the time of the event; it does not refer to an event which hypothetically might have caused death if it was more severe.

**Related** is defined as:

- A causal relationship between the intervention and an adverse event is at least a reasonable possibility, i.e. the relationship cannot be ruled out.

**Unexpected** is defined as:

- An adverse event which is not consistent with the information about the randomised imaging test (listed in 12.2.2)

# **12.2 OPERATIONAL DEFINITION & REPORTING PERIOD FOR AEs/SAEs**

#### 12.2.1 Expected AEs – Recorded in eCRF but not reportable

Due to the nature of heart failure and its treatment, patients are likely to experience adverse events throughout the course of the disease. The patient population may also have co-morbid disease and as such in this patient population, acute illness resulting in hospitalisation, new medical problems and deterioration of existing medical problems are expected. These events will be captured in the eCRF but will not be reportable.

#### 12.2.2 Related SAEs – Reported within standard eCRF

Related SAEs (expected and unexpected) for the randomised investigation alone that occur within 30 days will be collected. Adverse Events that occur during the hospitalisation for the procedure will be recorded in the eCRF but will not reported in an expedited manner unless unexpected.

Data to inform the objectives (deaths or hospitalisations) will be recorded from medical records but not designated as SAEs for both study arms outside of the SAE reporting period.

The following SAEs are expected within the trial population and will be reported by the clinical research teams using in the eCRF including:

- Angiography complications
  - Vascular complications
  - Peri-procedural stroke
  - o Peri-procedural MI
  - Allergic contrast reaction
- Allergic contrast reaction to either CTCA or stress CMR

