# 5. BACKGROUND

Each year 60,000 people are diagnosed with heart failure. In patients with neither history nor symptoms of coronary artery disease (CAD), occult CAD can still be identified in approximately 25% . Therefore, both NICE and European Society of Cardiology (ESC) guidelines recommend performing imaging to identify CAD . Whilst NICE does not specify the best test to identify CAD in heart failure there is guidance from ESC which only recommends either invasive coronary angiography (ICA) in intermediate-high risk patients (IIb, B) or CT coronary angiography (CTCA) in low-intermediate risk patients (IIa, C). Despite these recommendations there is widespread variation in practice with many patients not undergoing any investigations for CAD at all .

There is considerable variation in which imaging test, if any at all, is performed in patients presenting with heart failure in the NHS. This reflects a lack of clear evidence and variation in availability and expertise. There are no published data on the proportion of patients in the UK who undergo invasive angiography for investigation of heart failure, but registry data from Denmark and the USA suggest it may be between 17 and 35% . Despite advances in non-invasive imaging, registry data from Sweden suggests the proportion of patients with heart failure undergoing ICA is continuing to increase . In our own unpublished pilot data of 502 patients referred for CMR from multiple hospitals in West and North Yorkshire for the workup of presumed non-ischaemic cardiomyopathy 97 (19%) underwent invasive angiography. In a recent study from Leicester 24/46 (52%) with HFrEF and 27/140 (19%) with HFpEF underwent ICA .

ICA is often perceived to be the best test for the diagnosis of CAD, but it is expensive, has a serious complication rate of 1% and is uncomfortable for patients. We have carried out extensive patient and public involvement consultation and it is clear that most patients would prefer to avoid ICA if possible. Despite this ICA is still performed in approximately 20% of patients presenting with heart failure.

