It is possible to diagnose CAD using non-invasive cross-sectional imaging by CTCA or stress cardiovascular magnetic resonance (CMR). Both tests have been shown to have high sensitivity and specificity for identification of CAD in patients with angina pectoris  but the evidence to support their use in patients presenting specifically with heart failure is lacking.

The high sensitivity and specificity of CTCA (sensitivity 97%, specificity 78%) and stress CMR (sensitivity 90%, specificity 80%) compared to ICA is well established . However, there is very little evidence validating either test in patients presenting with heart failure. There are practical challenges in patients with heart failure that could impact the diagnostic accuracy such as poor contrast opacification in CTCA and reduced adenosine response in stress CMR. Therefore, there is a need to compare imaging pathways.

The only randomised evidence comparing cross sectional imaging modalities in heart failure is a study called IMAGE-HF conducted in Canada and Finland. In the CTCA portion (IMAGE-HF 1C) 246 patients were randomised to CTCA or ICA . 93/121 (77%) patients randomised to CTCA avoided the need for further downstream ICA. There was a trend to cost saving in the CTCA arm, but this did not reach significance. There was no difference in clinical outcomes or quality of life, although the study was underpowered for this. A recent meta-analysis of just 5 studies suggested a pooled sensitivity of 99% and specificity of 94% for CTCA compared to ICA. However, given the sample size of the individual studies and their heterogenous nature it is relatively weak evidence.

In IMAGE-HF 1B 500 patients with non-ischaemic heart failure were randomised to care with or without routine CMR . They found the addition of CMR did not add to the diagnostic yield compared to standard

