Patients undergoing CTCA or stress CMR may proceed to invasive angiography if deemed appropriate according to usual care. However, we will ask clinicians to avoid requesting the alternative non-invasive imaging test to minimise cross-over between arms.

**Co-enrolment to other trials:** Patients recruited to CROSS-HF will be allowed to be recruited to other trials, so long as it does not impact their participation in CROSS-HF. For example co-recruitment to STICH-3 BCIS-4, a NIHR funded trial comparing stenting and surgery for the management of patients with HF and LVEF≤40% will be possible. In usual care, the decision to choose between stents or surgery currently occurs following a discussion in a heart team meeting in the absence of evidence. In STICH-3 BCIS-4 assignment to stents or surgery will happen in a randomised manner in the trial. Co-recruitment to this trial will not affect any of the endpoints of CROSS-HF and will increase the chances of successful recruitment for both trials.

**Recruitment Rate:** The recruitment is planned over three and a half years (3 years assumed in sample size calculations, to compensate for ramping up of the recruitment at the start). Allowing for ramping up and the pilot phase, with 20 sites this equates to 5 randomisations per month per site.

**Follow up:** All follow up can be conducted remotely. Data for the primary and secondary endpoints (all cause death, myocardial infarction, heart failure hospitalisation, cardiovascular death, stroke, and revascularisation will be collected by review of primary and secondary care records at 6, 12 months and then annually for up to 4.5 years (or until 12 months after the last patient is recruited). Occasionally when information is not available in the medical records the site researchers may need to telephone patients for additional information.

Questionnaires including EuroQol EQ-5D-5L and Kansas City Cardiomyopathy Questionnaire (KCCQ) (see section 11.2) will be conducted at baseline, 6 and 12 months after randomisation. In addition, EuroQol EQ-5D-5L will be conducted annually for up to 4.5 years (or until 12 months after the last patient is recruited). Patient acceptability data will be collected at 6 months using a questionnaire created with input from the patient advisory group. A questionnaire on resource use will be collected at baseline and 12 months. With all questionnaires there will be the option to complete them on paper or online.

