#### 12.2.3 Related & Unexpected SAEs – Expedited Reporting

All Related & Unexpected SAEs occurring within 30 days of an investigation (angiography, stress CMR, CTCA) must be reported by the clinical research team in the eCRF within one working day of the investigator becoming aware of the event.

For each Related & Unexpected SAE the following information will be collected:

- full details in medical terms with a diagnosis, if possible
- its duration (start and end dates if applicable)
- action taken
- outcome
- causality (i.e. relatedness to investigation), in the opinion of the investigator

Any follow-up information should be added to the same Related & Unexpected Serious Adverse Event eCRF as soon as it is available. Events will be followed up until the event has resolved or a final outcome has been reached. All Related & Unexpected SAEs will be reviewed by the Chief Investigator and subject to expedited reporting to the Sponsor ([contact]) within 1 working day and the main REC on behalf of the Chief Investigator within 15 days.

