#### **12.2.5** Serious Adverse Events (SAEs) that Do Not Require Reporting

SAEs deemed to be unrelated to randomised investigation by the site PI (or delegated investigator) will not be reported.

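### The SAE rules disagree on whether complications of a downstream angiogram in the CTCA and stress CMR arms are collected; read literally, they tilt the exploratory complications comparison towards non-invasive imaging

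*Protocol*

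**What the plan says.** Five places in the Protocol bear on which complications are recorded.

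- Section 12.2.2 sets the collection rule: "Related SAEs (expected and unexpected) for the randomised investigation alone that occur within 30 days will be collected". The list of expected SAEs that follows names angiography complications (vascular, peri-procedural stroke, peri-procedural MI, contrast reaction) and contrast reactions to CTCA or stress CMR.
- Section 12.2.5 excludes by the same test: "SAEs deemed to be unrelated to randomised investigation by the site PI (or delegated investigator) will not be reported".
- Section 12.2.3 has a wider base and a narrower class of event: "All Related & Unexpected SAEs occurring within 30 days of an investigation (angiography, stress CMR, CTCA) must be reported".
- Section 12.1 defines 'unexpected' as "An adverse event which is not consistent with the information about the randomised imaging test (listed in 12.2.2").
- Section 11.3, under the unscheduled forms, describes the SAE form as "Serious Adverse Events (angiography complications and contrast reactions only"), with no restriction by arm.

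Section 10.2 makes downstream angiography part of the non-invasive pathways: "Patients undergoing CTCA or stress CMR may proceed to invasive angiography if deemed appropriate according to usual care". It also permits second-line testing or angiography after an inconclusive first test.

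Procedural complications are an exploratory outcome (section 13.3). Section 15.5 compares each non-invasive pathway with the invasive one, and section 15.1 analyses by the pathway allocated. Section 15.6 names procedural complications as an example of a mediator in an economic sensitivity analysis.

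**The concern.** The trial compares pathways, so the complications of a pathway should include those of every coronary test it leads to. The collection rule counts by test instead. A vascular complication of an angiogram is collected when angiography was the allocated test. On the literal rule it is not collected when the same procedure follows a CTCA or a stress CMR. For angiography harm the omission falls only on the two non-invasive arms, and it favours them.

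Avoiding the discomfort and risk of angiography is part of the protocol's stated reason for studying non-invasive tests (section 5), so a reader will look at this comparison even though it is exploratory. Events that sites are not asked to record at the time may be hard to recover consistently later. The follow-up forms in section 11.3 record that a further ICA took place, but they do not ask about its complications.

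**Working it through.** **Step 1. What happens to one event under each rule.** Take a complication of an angiogram that follows a CTCA or stress CMR.

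| Event | ICA arm | CTCA or CMR arm, sections 12.2.2 and 12.2.5 | CTCA or CMR arm, section 12.2.3 |
|---|---|---|---|
| Vascular complication | Collected, section 12.2.2 | Not collected: not caused by the randomised test | Reported only if classed as unexpected. Yes, if section 12.1 is applied to the letter; no, if the 12.2.2 list is taken as expected for the whole trial population, as that section introduces it |
| Contrast reaction | Collected, section 12.2.2 | Not collected, same reason | Most naturally expected, because contrast reactions are also listed for CTCA and CMR; so not reported |
| Peri-procedural MI or stroke | Collected, section 12.2.2 | Not collected as an SAE, but recorded as an MI or stroke under section 10.2 follow-up | As for a vascular complication |

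The form description in section 11.3 would admit all of these in any arm. Two sites could therefore treat the same event differently, each following the text.

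**Step 2. Inputs.**
- Downstream ICA after CTCA: section 5 reports that "93/121 (77%) patients randomised to CTCA avoided the need for further downstream ICA" in the earlier randomised CTCA trial.
- Serious complication rate of ICA: 1% (section 5).
- Arm size: 1000 per arm, so 1000 ICA against 2000 non-invasive (section 14).
- Downstream ICA after stress CMR: not given. It is assumed equal to the CTCA figure, with 10% to 50% as an assumed range.
- The 1% rate is assumed to apply equally to first-line and downstream angiograms, and everyone in the ICA arm is assumed to have the test.

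**Step 3. The protocol's own figure.** 93/121 = 76.9%, which agrees with the stated 77%. The complement is (121 - 93)/121 = 28/121 = 23.1%.

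**Step 4. Expected angiography complications.**
- ICA arm: 1000 × 0.01 = 10 per 1000, or 1.00%.
- Non-invasive arms, every angiogram counted: 0.231 × 0.01 = 0.00231, or 2.3 per 1000; over 2000 patients, about 4.6 events.
- Non-invasive arms, literal rule: 0.

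**Step 5. Effect on the risk difference (non-invasive minus ICA).**
- Full count: 0.23 - 1.00 = -0.77 percentage points.
- Literal rule: 0 - 1.00 = -1.00 percentage points.
- Shift: 0.23 points; 1.00/0.77 = 1.30, so the difference is overstated by about 30% in relative terms.

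**Step 6. Sensitivity to the downstream rate.**

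| Downstream ICA | Missed per 1000 non-invasive patients | Full-count difference (points) | Literal-rule difference (points) |
|---|---|---|---|
| 10% (assumed) | 1.0 | -0.90 | -1.00 |
| 23.1% (28/121) | 2.3 | -0.77 | -1.00 |
| 50% (assumed) | 5.0 | -0.50 | -1.00 |

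These are upper limits on what is lost. They treat every serious complication as missed, whereas peri-procedural MI and stroke still enter the trial data as events.

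**The case against.** The strongest reply is that the protocol does not settle that these complications go uncounted. The SAE form and the expected list name angiography complications without limiting them to the ICA arm. Section 12.2.3 covers any of the three tests. Applying section 12.1 to the letter turns a vascular complication in a CTCA-arm patient into an unexpected event that must be expedited. This stands: the defect is a contradiction about scope, and the omission follows only on the literal reading of sections 12.2.2 and 12.2.5. It does not remove the problem. The route through section 12.2.3 depends on how 'unexpected' is read, and it would put a routine complication through expedited reporting in two arms and standard recording in the third.

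A second reply is that safety reporting is not the outcome definition. No section says that the procedural-complications outcome, or the economic mediator, is drawn only from these SAE records, and the source may be set in the analysis plan. That also stands, so the effect on the economic work is only possible. But no other form described in the protocol asks for these complications.

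A reader might also infer that harm from stress agents or CT pre-medication is left out, because the SAE form mentions only angiography complications and contrast reactions. The documents do not support that. Such reactions arise from the randomised test, so the restriction in section 12.2.2 does not exclude them. They are absent from the expected list, so a serious related one is unexpected and reportable under section 12.2.3. What remains is that the form description in section 11.3 is narrower than sections 12.2.2 and 12.2.3.

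**Conclusion.** The SAE scope is internally contradictory and should be reconciled. Under the literal rule, expected-type complications of a downstream angiogram are collected in the ICA arm and not in the CTCA and CMR arms, which tilts one exploratory comparison, and possibly one economic sensitivity analysis, towards non-invasive imaging.

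The size is modest: at most about 2.3 events per 1000 non-invasive patients, and a shift from about -0.77 to -1.00 percentage points. The direction does not change anywhere in the 10% to 50% range. This rests on one earlier CTCA trial for the downstream rate, on carrying that rate over to stress CMR, and on the 1% complication rate applying to every angiogram.

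A reader might infer that the trial's main result is biased. It is not: death, MI and heart failure hospitalisation are collected from records in all arms whichever test preceded them (section 10.2), so the primary MACE comparison is unaffected.

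**What to change.** Change four places together; changing section 12.2.2 alone would leave sections 12.1 and 12.2.5 still excluding or reclassifying the downstream events.

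- Section 12.2.2: replace the restriction to the randomised test with *for the randomised investigation and any subsequent CTCA, stress CMR or invasive angiography, within 30 days of each, analysed by allocated arm*.
- Section 12.2.5: exclude only SAEs unrelated to any of those investigations.
- Section 12.1: judge 'unexpected' against the listed information for the investigation concerned, so that the same angiography complication is classed alike in all arms.
- Section 11.3: widen the SAE form description to match sections 12.2.2 and 12.2.3.

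Section 12.2.3 already has the right base and can stay. The cost is protocol wording, one eCRF form change and a few more related-SAE entries (about 4.6 expected over 2000 non-invasive patients on the figures above). Downstream tests are already recorded at follow-up, so sites can identify which patients to check.

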# **15.5 EXPLORATORY ANALYSES**

Procedural complications and time to diagnosis (which will be impacted by NHS waiting lists) will be compared between the two non-invasive pathways will each be compared for non-inferiority against invasive standard of care. Subsequently the two non-invasive pathways will be compared for superiority against each other.

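### Read literally, the related-SAE rule leaves out complications of downstream angiography in the CTCA and CMR arms, and other sections conflict with it

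*Protocol*

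**What the plan says.** Section 12.2.2 sets the scope: "Related SAEs (expected and unexpected) for the randomised investigation alone that occur within 30 days will be collected". Section 12.2.5 adds the exclusion: "SAEs deemed to be unrelated to randomised investigation by the site PI (or delegated investigator) will not be reported".

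Other sections are worded more widely, or at least differently:

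- Section 12.2.3, on expedited reporting: "All Related & Unexpected SAEs occurring within 30 days of an investigation (angiography, stress CMR, CTCA) must be reported". It names all three tests and does not say that the test must be the allocated one, but it covers only events that are both related and unexpected.
- Section 12.1 defines an unexpected event by reference to the randomised test and the list in 12.2.2.
- That list is introduced with "The following SAEs are expected within the trial population and will be reported by the clinical research teams". It gives vascular complications, stroke, MI and contrast reaction under angiography, but only allergic contrast reaction under CTCA and stress CMR.
- Section 11.3, under the unscheduled CRFs, describes the SAE form as "Serious Adverse Events (angiography complications and contrast reactions only", with no link to an arm.

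On the pathway, section 10.2 states: "Patients undergoing CTCA or stress CMR may proceed to invasive angiography if deemed appropriate according to usual care". On analysis, section 15.5 states "Procedural complications and time to diagnosis (which will be impacted by NHS waiting lists) will be compared", with each non-invasive pathway set against ICA. Section 15.3 analyses by allocated pathway, and section 15.6 names procedural complications as a possible mediator of costs and QALYs.

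**The concern.** The trial compares diagnostic strategies. An ICA prompted by a CTCA or stress CMR result is part of the non-invasive strategy, so harm from it belongs in that arm's count.

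A site that follows the scope sentence of 12.2.2 together with 12.2.5 would file an access-site bleed in a patient randomised to ICA. It would not file the same bleed after a downstream ICA in a patient randomised to CTCA, because the CTCA did not cause it. Ascertainment of angiography harm would then depend on the arm, and the error would run one way: ICA would look worse relative to non-invasive imaging than it is.

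At stake are the exploratory comparison of procedural complications and the mediator analysis in the economic evaluation. What is not recorded as it happens may be hard to recover. The follow-up forms in 11.3 record further cardiac tests and days in hospital for cardiovascular causes, but not complications of those tests.

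**Working it through.** **Step 1. One event traced through the text.** Take a vascular complication of an ICA done after a positive CTCA, in a patient randomised to CTCA.

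| Reading | Sections | Result |
|---|---|---|
| Scope limited to the randomised test | 12.2.2 first sentence, 12.2.5 | Not reported |
| Angiography complications expected across the whole trial population | 12.2.2 list, SAE form in 11.3 | Routine eCRF report |
| Not on the list for CTCA, so unexpected; any of the three tests counts | 12.1 with 12.2.3 | Expedited report |

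The same event in the ICA arm has one route: related, expected, filed on the standard eCRF.

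**Step 2. What is collected anyway.** Section 10.2 (Follow up) collects death, MI and stroke from records in all arms, whichever test was done. Under the narrow reading these events are still counted, but not labelled procedural. What can be lost is vascular complications and contrast reactions, and the link from an MI or stroke to a procedure.

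**Step 3. Size under the literal rule.** The protocol gives no figure for this point, so there is none to reproduce beyond the input. Inputs:

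- Serious complication rate of ICA: c = 1% (section 5).
- Downstream ICA after CTCA in the cited earlier trial: "93/121 (77%) patients randomised to CTCA avoided the need for further downstream ICA". Check: 93/121 = 76.9%, so d = 28/121 = 23.1% went on to ICA.
- Patients per arm: n = 1000 (section 14).
- Assumptions: everyone in the ICA arm has the test, and a downstream ICA carries the same 1% rate.

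ICA arm: n × c = 1000 × 0.01 = 10 events.

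CTCA arm, from downstream ICA: n × d × c = 1000 × 0.231 × 0.01 = 2.3 events.

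Difference with full capture: c × (1 − d) = 1% × 0.769 = 0.77 percentage points.

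Difference if all downstream events are lost: c = 1.00 percentage point.

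Overstatement: 1/(1 − d) − 1 = d/(1 − d) = 28/93 = 30%. It does not depend on c.

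**Step 4. Range.** The protocol gives no downstream ICA share for stress CMR, and the CTCA figure comes from one trial, so d is varied by assumption.

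| d | Events lost per 1000 | Full-capture difference (points) | Overstatement |
|---|---|---|---|
| 10% | 1.0 | 0.90 | 11% |
| 23.1% | 2.3 | 0.77 | 30% |
| 40% | 4.0 | 0.60 | 67% |

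These are upper limits for each d. The 1% is not broken down by type, and any deaths, MIs and strokes within it are recorded as outcomes.

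**The case against.** The strongest reply is that the protocol does not settle on non-collection:

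- By the definition in 12.1, an access-site complication in a CTCA patient is unexpected, so 12.2.3 may pick it up.
- The SAE form and the 12.2.2 list are not tied to an arm.
- Relatedness in 12.1 means only that a causal link cannot be ruled out, and an investigator might judge harm from an ICA prompted by the randomised CTCA to be related to it.
- Section 12.2.1 also speaks of capturing hospitalisations in the eCRF.
- The operational definition of procedural complications may sit in the analysis plan.

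Much of this stands. A reader might infer that no downstream angiography harm is recorded, giving 10 events against 0 and an apparent 100% reduction instead of 77%. The documents do not support that. It is the extreme of one reading, and it ignores the outcome collection of death, MI and stroke in every arm. Nor can one say that safety reviewers would never see these events.

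The narrow wording also leaves out second-line tests in the ICA arm, which 10.2 allows after an inconclusive result. It is therefore not true that every test-related harm in that arm is counted.

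The effect is small beside sampling error. With 10 and 2.3 events per 1000, the 95% half-width of the difference is about 1.96 × √(0.01 × 0.99/1000 + 0.0023 × 0.9977/1000) = 0.7 points, against a possible error of 0.23.

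The reply does not remove the conflict. The scope sentence is explicit and 12.2.5 repeats it. Section 12.2.3 helps only if the site calls the event unexpected, while the 12.2.2 list calls angiography complications expected in the trial population. Form content and a list of expected events do not plainly override a stated scope.

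**Conclusion.** The point holds as a conflict between sections that permits arm-dependent recording, not as proven non-collection. On the literal wording of 12.2.2 and 12.2.5, complications of a downstream ICA fall outside related-SAE collection in two arms, while the same events are collected in the third. The firm gap is vascular complications and contrast reactions, and the procedural label on MI and stroke.

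Under the literal rule the recorded difference between ICA and CTCA is overstated by up to 0.23 percentage points, or about 30% (11% to 67% for a downstream share of 10% to 40%). This rests on the protocol's 1% rate, the same rate for downstream ICA, and 23% from one earlier CTCA trial. Any figure for stress CMR is an assumption.

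The outcome is exploratory. A reader might extend the bias to the main result, but the primary MACE endpoint does not depend on SAE reporting and is unaffected. The point still deserves action: the error has a known direction, it concerns the harm that section 5 cites against ICA, and it is cheap to prevent now.

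**What to change.** Reconcile the SAE form description in 11.3 with sections 12.1, 12.2.2, 12.2.3 and 12.2.5 so that they share one scope. Related SAEs within 30 days of the randomised test, or of any subsequent CTCA, stress CMR or ICA in the diagnostic pathway, are collected identically in all three arms. Define expectedness by the procedure that caused the event, so that the same event takes the same route in every arm. Record the causing procedure on the form, and tabulate procedural complications by randomised arm.

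The cost is a wording change, one extra eCRF field and a few more SAE forms: on the figures above, about 2 in the CTCA arm over the whole trial (1 to 4 per non-invasive arm across the assumed range).
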